Appendix C Summary of statistical analyses

Endpoint	Analysis		Statistical	Supportive	Subgroup	Other
	Population	Primary Analysis	Method	Analysis*	Analysis*	Analyses*
Primary Endpoint						
Patients who achieved sustained remission at Week 52	ITT	Proportion of patients achieving sustained remission at Week 52	CMH test stratified by baseline prednisone dose for combined groups, and descriptive analysis for non-combined groups.	1) Sensitivity analysis;2) Analysis excluding patients who prematurely withdraw from the study due to early termination of the study	No	No
Additional endpoint: Patients who achieved sustained remission at Week 24	ITT	Proportion of patients achieving sustained remission at Week 24	CMH test stratified by baseline prednisone dose for combined groups, and descriptive analysis for non-combined groups	Sensitivity analysis	No	No
Secondary Endpoints						
Patients who achieved of disease remission by Week 12	ITT	Proportion of patients who achieved of disease remission by Week 12	Descriptive	No	No	No
Patients who have absence of disease flare from Week 12 through Week 24 and Week 52	ITT	Proportion of patients who have absence of disease flare from Week 12 through Week 24 and Week 52	Descriptive	No	No	No
Patients who have normalization of CRP (decrease to <10 mg/L) with sustained normalization from Week	ITT	Proportion of patients who have normalization of CRP (decrease to <10 mg/L) with sustained normalization from Week 12 through Week 24 and Week 52	Descriptive	No	No	No

Endpoint	Analysis		Statistical	Supportive	Subgroup	Other
	Population	Primary Analysis	Method	Analysis*	Analysis*	Analyses*
12 through Week 24 and Week 52						
Patients who successfully adhere to the prednisone taper from Week 12 through Week 24 and Week 52	ITT	Proportion of patients who successfully adhere to the prednisone taper from Week 12 through Week 24 and Week 52	Descriptive	No	No	No
Total cumulative prednisone (or equivalent) dose	ITT	Total cumulative prednisone (or equivalent) dose over 52-week treatment period	Descriptive	No	No	No
Time to the first GCA flare after clinical remission up to Week 52	ITT	Time (from randomization) to the first GCA flare after clinical remission up to Week 52	Kaplan-Meier estimates and Cox proportional hazards model for combined groups, and descriptive analysis for non-combined groups.	No	No	No
Total composite GTI total score	ITT	Cumulative GTI scores (CWS and AIS) at Week 24 and Week 52	Descriptive by 4 treatment groups; and analysis of covariance (ANCOVA) model for combined groups.	No	No	Summaries of domain specific scores and specific list events at Week 12, 24, 40 and 52.
Safety						
Adverse Events	Safety	Follow safety guidelines	Descriptive	No	No	No
Laboratory	Safety	Follow safety guidelines	Descriptive	No	No	No
Vital signs and ECGs	Safety	Follow safety guidelines	Descriptive	No	No	No

Endpoint	Analysis		Statistical	Supportive	Subgroup	Other
	Population	Primary Analysis	Method	Analysis*	Analysis*	Analyses*
PK						
Sarilumab serum concentration	PK	By visit	Descriptive	No	No	No
Immunogenicity						
ADA positive patients	ADA	NA	Descriptive	No	No	No
ADA negative patients	ADA	NA	Descriptive	No	No	No
Persistent ADA response	ADA	NA	Descriptive	No	No	No
Transient ADA response	ADA	NA	Descriptive	No	No	No

Appendix D SF-36 V2 Scoring

General Scoring information

Items and scales are scored in 3 steps:

- Step 1. Item recoding, for the 10 items that require recoding,
- Step 2. Computing scale scores by summing across items in the same scale (raw scale scores); and,
- Step 3. Transforming raw scale scores to a 0-100 scale (transformed scale).

Item recoding

- All 36 items should be checked for out-of-range values prior to assigning the final item value. All out-of-range values should be recoded as missing data.
- The following tables show the recoding of response choice.

How to treat missing data

A scale score is calculated if a respondent answered at least half of the items in a multi-item scale (or half plus one in the case of scales with an odd number of items).

The recommended algorithm substitutes a person-specific estimate for any missing item when the respondent answered at least 50 percent of the items in a scale. A psychometrically sound estimate is the average score, across completed items in the same scale, for that respondent. For example, if a respondent leaves one item in the 5-item mental Health scale blank, substitute the respondent's average score (across the 4 completed mental health items) for that one item. When estimating the respondent's average score, use the respondent's final item values.

Computing raw scale scores

After item recoding, including handling of missing data, a raw score is computed for each scale. This score is a simple algebraic sum of responses for all items in that scale.

If the respondent answered at least 50% of the items in a multi-items scale, the score can be calculated. If the respondent did not answer at least 50% of the items, the score for that scale should be set to missing.

Transformation of the scale scores

The next step involves transforming each raw score to a 0 to 100 scale using the following formula:

$$\text{Transformed scale} = \frac{[(\text{actual raw score} - \text{lowest possible raw score}) / \text{possible raw score range}] \times 100}{100}$$

This transformation converts the lowest and highest possible scores to zero and 100, respectively.

Table 8 - SF-36 V2 raw scores of eight domains

Scale	Lowest and highest possible raw scores	Possible raw score range
Physical Functioning	10,30	20
Role-Physical	4,20	16
Bodily pain	2,12	10
General health	5,25	20
Vitality	4,20	16
Social Functioning	2,10	8
Role-Emotional	3,15	12
Mental Health	5,25	20

Appendix E FACIT-fatigue scoring guidelines (version 4)

- Instructions:*
1. Record answers in "item response" column. If missing, mark with an X
 2. Perform reversals as indicated, and sum individual items to obtain a score.
 3. Multiply the sum of the item scores by the number of items in the subscale, then divide by the number of items answered. This produces the subscale score.
 4. The higher the score, the better the QOL.

Subscale	Item Code	Reverse item?	Item response	Item Score
FATIGUE	HI7	4 -	_____	= _____
	SUBSCALE	HI12	4 -	_____
	An1	4 -	_____	= _____
	An2	4 -	_____	= _____
	An3	4 -	_____	= _____
	An4	4 -	_____	= _____
	An5	0 +	_____	= _____
	An7	0 +	_____	= _____
	An8	4 -	_____	= _____
	An12	4 -	_____	= _____
	An14	4 -	_____	= _____
	An15	4 -	_____	= _____
	An16	4 -	_____	= _____

Sum individual item scores: _____

Multiply by 13: _____

Divide by number of items answered: _____ = **Fatigue Subscale score**

*For guidelines on handling missing data and scoring options, please refer to the Administration and Scoring Guidelines in the manual or on-line at www.facit.org.

Appendix F SAS code for EQ-5D-3L index utility scoring

```
/*=====*/;
/* Aim : Derive the EQ5-D index (utility) */;
/* Source for the algorithm : scoring EQ-5D health states (Rosalind Rabin */;
/* (cf. G:\_HE\PRO questionnaire\EQ5D\scoring\YorkTariffx.doc) */;
/* Note : UK based population (Dolan, 1997) */;
/* Author : [name] */;
/*=====*/;

data EUROQOL; set temp;
profil= (10000*eqq1cd)+(1000*eqq2cd)+(100*eqq3cd)+(10*eqq4cd)+eqq5cd;
eq5d=1;
*****Mobility*****;
if eqq1cd=2 then eq5d=eq5d-0.069;
if eqq1cd=3 then eq5d=eq5d-0.314;
*****Self-care*****;
if eqq2cd=2 then eq5d=eq5d-0.104;
if eqq2cd=3 then eq5d=eq5d-0.214;
*****Usual activities*****;
if eqq3cd=2 then eq5d=eq5d-0.036;
if eqq3cd=3 then eq5d=eq5d-0.094;
*****Pain/discomfort*****;
if eqq4cd=2 then eq5d=eq5d-0.123;
if eqq4cd=3 then eq5d=eq5d-0.386;
*****Anxiety/depression*****;
if eqq5cd=2 then eq5d=eq5d-0.071;
if eqq5cd=3 then eq5d=eq5d-0.236;

if (eqq1cd ne 1 or eqq2cd ne 1 or eqq3cd ne 1 or eqq4cd ne 1 or eqq5cd ne 1)
then eq5d=eq5d-0.081;

if (eqq1cd=3 or eqq2cd=3 or eqq3cd=3 or eqq4cd=3 or eqq5cd=3)
then eq5d=eq5d-0.269;

if (eqq1cd=. or eqq2cd=. or eqq3cd=. or eqq4cd=. or eqq5cd=.)
then eq5d=.;

run;
```

Appendix G SAS code for SF-36 scoring

```
*****
* PROGRAM: SF36 V2
* PURPOSE: SAS SCORING PROGRAM FOR THE SF-36 VERSION2
*
*****;

*****;
*** STEP 1: INPUT DATA ***;
*****;

DATA SF36DATA;
INFILE IN;
INPUT ID $ 1-3
      @ 5 (GH1 HT PF01-PF10 RP1-RP4 RE1-RE3 SF1
          BP1-BP2 VT1 MH1 MH2 MH3 VT2 MH4 VT3 MH5
          VT4 SF2 GH2 GH3 GH4 GH5) (1.);
RUN;

*****;
*** STEP 2: SF-36 SCALE CONSTRUCTION ***;
*****;

*****
* USING THE SAS DATASET CREATED IN PART 1, CHANGE OUT-OF-RANGE
* VALUES TO MISSING FOR EACH ITEM. RECODE AND RECALIBRATE ITEMS
* AS NEEDED. AN 'R' PREFIX MEANS THE VARIABLE IS RECODED.
*****;

DATA SF36SCAL;
SET SF36DATA;

*****
* THE SF-36 PHYSICAL FUNCTIONING INDEX.
* ALL ITEMS ARE POSITIVELY SCORED -- THE HIGHER THE ITEM
* VALUE, THE BETTER THE PHYSICAL HEALTH.
*
* THIS SCALE IS POSITIVELY SCORED.
* THE HIGHER THE SCORE THE BETTER THE PHYSICAL FUNCTIONING.
*****;

ARRAY PFI(10) PF01-PF10;

DO I = 1 TO 10;
IF PFI(I) < 1 OR PFI(I) > 3 THEN PFI(I) = .;
END;

PFNUM = N(OF PF01-PF10);
PFMEAN = MEAN(OF PF01-PF10);

DO I = 1 TO 10;
IF PFI(I) = . THEN PFI(I) = PFMEAN;
```

END;

IF PFNUM GE 5 THEN RAWPF = SUM(OF PF01-PF10);
PF = ((RAWPF - 10)/(30-10)) * 100;

LABEL PF = 'SF-36 PHYSICAL FUNCTIONING (0-100)'
RAWPF = 'RAW SF-36 PHYSICAL FUNCTIONING';

* THE SF-36 ROLE-PHYSICAL INDEX.
* ALL ITEMS ARE POSITIVELY SCORED -- THE HIGHER THE ITEM VALUE,
* THE BETTER THE ROLE-PHYSICAL FUNCTIONING.
*
* THIS SCALE IS POSITIVELY SCORED.
* THE HIGHER THE SCORE THE BETTER THE ROLE-PHYSICAL.
*****;

ARRAY RPA(4) RP1-RP4;

DO I = 1 TO 4;
IF RPA(I) < 1 OR RPA(I) > 5 THEN RPA(I) = .;
END;

ROLPNUM = N(OF RP1-RP4);
ROLPMEAN = MEAN(OF RP1-RP4);

DO I = 1 TO 4;
IF RPA(I) = . THEN RPA(I) = ROLPMEAN;
END;

IF ROLPNUM GE 2 THEN RAWRP = SUM(OF RP1-RP4);
RP = ((RAWRP - 4)/(20-4)) * 100;
LABEL RP = 'SF-36 ROLE-PHYSICAL (0-100)'
RAWRP = 'RAW SF-36 ROLE-PHYSICAL';

* THE SF-36 PAIN ITEMS.
* ITEM RECODING DEPENDS ON WHETHER BOTH PAIN1 AND PAIN2
* ARE ANSWERED OR WHETHER ONE OF THE ITEMS HAS MISSING DATA.
* AFTER RECODING, ALL ITEMS ARE POSITIVELY SCORED -- THE HIGHER
* THE SCORE, THE LESS PAIN (OR THE MORE FREEDOM FROM PAIN).
*
* THIS SCALE IS POSITIVELY SCORED. THE HIGHER THE
* SCORE THE LESS PAIN OR THE MORE FREEDOM FROM PAIN.
*****;

IF BP1 < 1 OR BP1 > 6 THEN BP1 = .;
IF BP2 < 1 OR BP2 > 5 THEN BP2 = .;

* RECODES IF NEITHER BP1 OR BP2 HAS A MISSING VALUE;

IF BP1 NE . AND BP2 NE . THEN DO;

IF BP1 = 1 THEN RBP1 = 6;

```
IF BP1 = 2 THEN RBP1 = 5.4;
IF BP1 = 3 THEN RBP1 = 4.2;
IF BP1 = 4 THEN RBP1 = 3.1;
IF BP1 = 5 THEN RBP1 = 2.2;
IF BP1 = 6 THEN RBP1 = 1;

IF BP2 = 1 AND BP1 = 1 THEN RBP2 = 6;
IF BP2 = 1 AND 2 LE BP1 LE 6 THEN RBP2 = 5;
IF BP2 = 2 AND 1 LE BP1 LE 6 THEN RBP2 = 4;
IF BP2 = 3 AND 1 LE BP1 LE 6 THEN RBP2 = 3;
IF BP2 = 4 AND 1 LE BP1 LE 6 THEN RBP2 = 2;
IF BP2 = 5 AND 1 LE BP1 LE 6 THEN RBP2 = 1;

END;

* RECODES IF BP1 IS NOT MISSING AND BP2 IS MISSING;

IF BP1 NE . AND BP2 = . THEN DO;
  IF BP1 = 1 THEN RBP1 = 6;
  IF BP1 = 2 THEN RBP1 = 5.4;
  IF BP1 = 3 THEN RBP1 = 4.2;
  IF BP1 = 4 THEN RBP1 = 3.1;
  IF BP1 = 5 THEN RBP1 = 2.2;
  IF BP1 = 6 THEN RBP1 = 1;
  RBP2 = RBP1;
END;

* RECODES IF BP1 IS MISSING AND BP2 IS NOT MISSING;

IF BP1 = . AND BP2 NE . THEN DO;
  IF BP2 = 1 THEN RBP2 = 6;
  IF BP2 = 2 THEN RBP2 = 4.75;
  IF BP2 = 3 THEN RBP2 = 3.5;
  IF BP2 = 4 THEN RBP2 = 2.25;
  IF BP2 = 5 THEN RBP2 = 1;
  RBP1 = RBP2;
END;

BPNUM = N(BP1,BP2);

IF BPNUM GE 1 THEN RAWBP = SUM(RBP1,RBP2);
BP = ((RAWBP - 2)/(12-2)) * 100;

LABEL BP = 'SF-36 PAIN INDEX (0-100)'
      RAWBP = 'RAW SF-36 PAIN INDEX';

*****
* THE SF-36 GENERAL HEALTH PERCEPTIONS INDEX.
* REVERSE TWO ITEMS AND RECALIBRATE ONE ITEM. AFTER RECODING
* AND RECALIBRATION, ALL ITEMS ARE POSITIVELY SCORED -- THE
* HIGHER THE SCORE, THE BETTER THE PERCEIVED GENERAL HEALTH.
*
```

* THIS SCALE IS POSITIVELY SCORED.
* THE HIGHER THE SCORE THE BETTER THE HEALTH PERCEPTIONS.
*****;

ARRAY GHP(5) GH1-GH5;

DO I= 1 TO 5;
IF GHP(I) < 1 OR GHP(I) > 5 THEN GHP(I) = .;
END;

IF GH1 = 1 THEN RGH1 = 5;
IF GH1 = 2 THEN RGH1 = 4.4;
IF GH1 = 3 THEN RGH1 = 3.4;
IF GH1 = 4 THEN RGH1 = 2;
IF GH1 = 5 THEN RGH1 = 1;

RGH3 = 6 - GH3;
RGH5 = 6 - GH5;

GHNUM = N(GH1, GH2, GH3, GH4, GH5);
GHMEAN = MEAN(RGH1, GH2, RGH3, GH4, RGH5);

ARRAY RGH(5) RGH1 GH2 RGH3 GH4 RGH5;

DO I= 1 TO 5;
IF RGH(I) = . THEN RGH(I) = GHMEAN;
END;

IF GHNUM GE 3 THEN RAWGH = SUM(RGH1, GH2, RGH3, GH4, RGH5);
GH = ((RAWGH - 5) / (25-5)) * 100;

LABEL GH = 'SF-36 GENERAL HEALTH PERCEPTIONS (0-100)'
RAWGH = 'RAW SF-36 GENERAL HEALTH PERCEPTIONS';

* THE SF-36 VITALITY ITEMS.
* REVERSE TWO ITEMS. AFTER ITEM REVERSAL, ALL ITEMS ARE
* POSITIVELY SCORED -- THE HIGHER THE SCORE, THE LESS THE FATIGUE
* AND THE GREATER THE ENERGY.
*
* THIS SCALE IS POSITIVELY SCORED.
* THE HIGHER THE SCORE THE GREATER THE VITALITY.
*****;

ARRAY VI(4) VT1-VT4;

DO I = 1 TO 4;
IF VI(I) < 1 OR VI(I) > 5 THEN VI(I) = .;
END;

RVT1 = 6-VT1;
RVT2 = 6-VT2;

VITNUM = N(VT1, VT2, VT3, VT4);
VITMEAN = MEAN(RVT1, RVT2, VT3, VT4);

```
ARRAY RVI(4) RVT1 RVT2 VT3 VT4;
```

```
DO I = 1 TO 4;  
  IF RVI(I) = . THEN RVI(I) = VITMEAN;  
END;
```

```
IF VITNUM GE 2 THEN RAWVT= SUM(RVT1,RVT2,VT3,VT4);  
VT = ((RAWVT-4)/(20-4)) * 100;
```

```
LABEL VT = 'SF-36 VITALITY (0-100)'  
  RAWVT = 'RAW SF-36 VITALITY';
```

```
*****  
* THE SF-36 SOCIAL FUNCTIONING INDEX.  
* REVERSE ONE ITEM SO THAT BOTH ITEMS ARE POSITIVELY SCORED --  
* THE HIGHER THE SCORE, THE BETTER THE SOCIAL FUNCTIONING.  
*  
* THIS SCALE IS POSITIVELY SCORED.  
* THE HIGHER THE SCORE THE BETTER THE SOCIAL FUNCTIONING.  
*****;
```

```
ARRAY SOC(2) SF1-SF2;
```

```
DO I = 1 TO 2;  
  IF SOC(I) < 1 OR SOC(I) > 5 THEN SOC(I) = .;  
END;
```

```
RSF1 = 6 - SF1;  
SFNUM = N(SF1,SF2);  
SFMEAN = MEAN(RSF1,SF2);
```

```
ARRAY RSF(2) RSF1 SF2;
```

```
DO I = 1 TO 2;  
  IF RSF(I) = . THEN RSF(I) = SFMEAN;  
END;
```

```
IF SFNUM GE 1 THEN RAWSF = SUM(RSF1,SF2);  
SF = ((RAWSF - 2)/(10-2)) * 100;
```

```
LABEL SF = 'SF-36 SOCIAL FUNCTIONING (0-100)'  
  RAWSF = 'RAW SF-36 SOCIAL FUNCTIONING';
```

```
*****  
* THE SF-36 ROLE-EMOTIONAL INDEX.  
* ALL ITEMS ARE POSITIVELY SCORED -- THE HIGHER THE ITEM VALUE,  
* THE BETTER THE ROLE-EMOTIONAL FUNCTIONING.  
*  
* THIS SCALE IS POSITIVELY SCORED.  
* THE HIGHER THE SCORE, THE BETTER THE ROLE-EMOTIONAL.  
*****;
```

```
ARRAY RM(3) RE1-RE3;
```

```
DO I = 1 TO 3;
  IF RM(I) < 1 OR RM(I) > 5 THEN RM(I) = .;
END;

ROLMNUM = N(OF RE1-RE3);
ROLMMEAN = MEAN(OF RE1-RE3);

DO I = 1 TO 3;
  IF RM(I) = . THEN RM(I) = ROLMMEAN;
END;

IF ROLMNUM GE 2 THEN RAWRE = SUM(OF RE1-RE3);
RE = ((RAWRE - 3)/(15-3)) * 100;

LABEL RE = 'SF-36 ROLE-EMOTIONAL (0-100)'
      RAWRE = 'RAW SF-36 ROLE-EMOTIONAL';

*****
* THE SF-36 MENTAL HEALTH INDEX.
* REVERSE TWO ITEMS. AFTER ITEM REVERSAL, ALL ITEMS ARE
* POSITIVELY SCORED -- THE HIGHER THE SCORE, THE BETTER THE
* MENTAL HEALTH.
*
* THIS SCALE IS POSITIVELY SCORED.
* THE HIGHER THE SCORE THE BETTER THE MENTAL HEALTH.
*****;

ARRAY MHI(5) MH1-MH5;

DO I = 1 TO 5;
  IF MHI(I) < 1 OR MHI(I) > 5 THEN MHI(I)=.;
END;

RMH3 = 6-MH3;
RMH5 = 6-MH5;

MHNUM=N(MH1,MH2,MH3,MH4,MH5);
MHMEAN=MEAN(MH1,MH2,RMH3,MH4,RMH5);

ARRAY RMH(5) MH1 MH2 RMH3 MH4 RMH5;

DO I = 1 TO 5;
  IF RMH(I) = . THEN RMH(I) = MHMEAN;
END;

IF MHNUM GE 3 THEN RAWMH = SUM(MH1,MH2,RMH3,MH4,RMH5);
MH = ((RAWMH-5)/(25-5)) * 100;

LABEL MH = 'SF-36 MENTAL HEALTH INDEX (0-100)'
      RAWMH = 'RAW SF-36 MENTAL HEALTH INDEX';

*****
* THE SF-36 HEALTH TRANSITION ITEM.
```

```
* THIS ITEM SHOULD BE ANALYZED AS CATEGORICAL DATA,  
* PENDING FURTHER RESEARCH.  
*****;  
  
IF HT < 1 OR HT > 5 THEN HT = .;  
  
LABEL HT='RAW SF-36 HEALTH TRANSITION ITEM';  
RUN;  
  
*****;  
*** STEP 3: SF-36 SCALE CONSTRUCTION ***;  
*****;  
  
DATA SF36INDX;  
SET SF36SCAL;  
  
*****;  
* purpose: create physical and mental health index scores  
* standardized but not normalized  
* and standard deviations calculated with vardef=wdf  
*****;  
  
/*****/  
/* NORM-BASED SCORING OF SF-36, STANDARD RECALL (4 WEEKS) */  
/* USING WEIGHTED MEANS AND SD'S FROM 1998 GENERAL US POPULATION */  
/* FROM COMBINED SAMPLES */  
/*****/  
  
*****  
*****1998 US NORMS*****  
*****;  
  
*CREATING SF-36 STANDARDIZED SCORES (0-100 Means/SD's from 1998 General  
Population)*;  
  
pf_z=(pf-83.29094)/23.75883;  
rp_z=(rp-82.50964)/25.52028;  
bp_z=(bp-71.32527)/23.66224;  
gh_z=(gh-70.84570)/20.97821;  
vt_z=(vt-58.31411)/20.01923;  
sf_z=(sf-84.30250)/22.91921;  
re_z=(re-87.39733)/21.43778;  
mh_z=(mh-74.98685)/17.75604;  
  
*****;  
* COMPUTE SAMPLE RAW FACTOR SCORES *;  
* Z SCORES ARE FROM ABOVE *;  
* SCORING COEFFICIENTS ARE FROM U.S. GENERAL POPULATION *;  
* FACTOR ANALYTIC SAMPLE N=2393: HAVE ALL EIGHT SCALES *;  
*****;
```

```
praw=(pf_z * .42402)+(rp_z * .35119)+(bp_z * .31754)+(sf_z * -.00753)+  
      (mh_z * -.22069)+(re_z * -.19206)+(vt_z * .02877)+(gh_z * .24954);  
  
mraw=(pf_z * -.22999)+(rp_z * -.12329)+(bp_z * -.09731)+(sf_z * .26876)+  
      (mh_z * .48581)+(re_z * .43407)+(vt_z * .23534)+(gh_z * -.01571);  
  
*COMPUTE AGGREGATE STANDARDIZED SUMMARY SCORES*;  
  
PCS = (praw*10) + 50;  
MCS = (mraw*10) + 50;  
  
label PCS='STANDARDIZED PHYSICAL COMPONENT SCALE-00'  
      MCS='STANDARDIZED MENTAL COMPONENT SCALE-00';  
  
run;
```

Appendix H Visit windows based on day ranges

Visit windows based on days relative to the first IMP dose will be used to map (see [Table 9](#)).

Table 9 - Day range for each scheduled visit in the DB period for efficacy, lab, vital sign, PK and ADA summaries

Visit Label	Target Day	Schedule A ^a	Schedule B ^b	Schedule C ^c	Schedule D ^d	Schedule E ^e	Schedule F ^f	Schedule G ^g	Schedule H ^h	Schedule I ⁱ	Schedule J ^j
Double-Blind Period											
Baseline	1	≤1	≤ 1	≤ 1	≤ 1	≤ 1		≤ 1	≤ 1	≤ 1	≤ 1
Week 2	15	>1'- 21							>1'-21	>1'-49	
Week 4	29	22-42				>1'-56	>1'-56	>1'-42	22 - 56		>1'-98
Week 8	57	43-70						43 - 70			
Week 12	85	71-98	>1'-126	>1'-126		57 - 126	57 - 126	71 - 98	57 - 98	50 - 126	
Week 16	113	99-126						99 - 126	99 - 140		
Week 20	141	127-154						127 - 154			
Week 24	169	155-196	127 - 224	127 - 266		127 - 224	127 - 224	155 - 196	141 - 266	127 - 266	≥ 99
Week 32	225	197-252						197 - 252			
Week 40	281	253-322	225 - 322			225 - 322	225 - 322	253 - 322			
Week 52	365	≥323	≥ 323	≥ 267	>1'	≥ 323	≥ 323	≥ 323	≥ 267	≥ 267	

a Includes temperature, heart rate, blood pressure, GCA clinical assessments (including disease flare), CRP, ESR

b Includes weight, glucocorticoid toxicity index (excluding bone density assessment)

c Includes physician global assessments (MD-VAS), patient reported outcomes and antibodies to sarilumab/ADA

d Includes bone density assessment, ANA

e Includes hematology: hemoglobin, hematocrit, red blood cell (RBC) count and morphology (if RBC count is abnormal), white blood cell (WBC) differential, platelet count, absolute neutrophil count (ANC) and chemistry: sodium, potassium, calcium, chloride, bicarbonate, total protein, creatinine and clearance, blood urea nitrogen (BUN), uric acid, lactate dehydrogenase (LDH), phosphate, albumin, ALT (SGPT), AST (SGOT), alkaline phosphatase (ALP), total bilirubin, conjugated bilirubin, and unconjugated bilirubin

f Includes HbA1c, fasting glucose, fasting lipids: triglycerides (TG), total cholesterol, HDL, LDL

g Includes urine pregnancy test

h Includes serum sarilumab

i Includes biomarkers-IL-6 and sIL-6R

j Includes immune cell phenotyping (whole blood)

* Includes value measured on day 1 but after the first IMP dose

For PK and ADA, the follow-up (i.e., 6-week post-treatment) measurement will be defined based on the sample collected at the follow-up visit (ie, Visit 13). The rests of PK and ADA measurements will be mapped to each visit using the visit window defined in [Table 9](#).

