During the course of study, for patients in need of rescue therapy as per Investigator judgment, CS should be the agent of first choice. Patients may continue SC administration of sarilumab or matching placebo only if CS is used as the rescue therapy. If the patients remain symptomatic despite CS rescue therapy, then other treatment options including nonbiological immunosuppressive drugs may be used and the patient must be discontinued from the study treatment and considered a non-responder.

If the patient or Investigator decides to discontinue the administration of blinded sarilumab injections, then the patient will be asked to return to the site for study assessments as per protocol until end of study (EOS) evaluation, unless the patient cannot or does not wish to continue the assessments, in which case an early withdrawal visit and safety follow up should be performed. It is recommended that patients complete Visit 13, if possible.

Total duration of study participation for each patient is up to 82 weeks:

- Up to 6 weeks screening period.
- 52-week treatment period (sarilumab or placebo, double-blind phase).
- 24-week post treatment follow-up period.

The last patient last visit will occur when the last patient has completed the 24-week follow up period (EOS). The end of the clinical trial is defined as the last patient's last visit.

Study discontinuation plan

As mentioned in [Section 1](#), due to the protracted recruitment timeline and internal portfolio reprioritization, Sanofi has decided to terminate the EFC15068 study in July 2020. For patients who were already enrolled with ongoing treatment in the study, investigators were instructed to discontinue the study drugs and transition these patients into post-treatment follow-up period for safety assessments. The study discontinuation plan is as follows:

- All randomized patients should stop by 12 weeks from the date of announcement to the sites and should be scheduled for the end of study treatment visit at their earliest

convenience and no later than *October 13, 2020*, which would ensure sufficient time for patients to identify alternative therapy as needed.

- All patients will have a follow-up (EOS) visit that is 6 weeks after treatment cessation and no later than *November 24, 2020*.

Thus, the last patient last visit will occur when the last patient has completed the 6-week follow-up period (EOS). The end of the clinical trial is defined as the last patient's last visit.

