2.4.7 Analyses of quality of life variables

Descriptive statistics including number of subjects, mean, median, SD, minimum, maximum will be provided by treatment groups for the value and change from baseline at each visit (baseline, Week 12, Week 24 and Week 52) for the 2 summary measures of SF-36 (physical component summary score and mental component summary score) and the 8 domains, the quantitative variables of EQ-5D-3L (visual analog scale and single index utility), FACIT-Fatigue, HAQ-DI (standardized score, pain score and patient global assessment) and MD-VAS. Analyses will be performed based on data as observed; no missing data will be imputed.

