2.5.4 Windows for time points

Visit windows based on days relative to the first IMP dose will be used to map the efficacy, lab, vital signs, PK and ADA measurements to each scheduled visit (see [Appendix H](#)). The following rule will be applied when mapping the measurements to the visit:

- For the same parameter (i.e., efficacy, lab, or vital signs), if a patient has more than one measurement at different dates within the same visit window, the scheduled measurement that is closest to the target date will be used (in case of tie select the latest). If there is no scheduled measurement within the visit window, the unscheduled measurement that is closest to the target date will be used (in case of tie select the latest).
- When a patient has more than one measurement on the same parameter on the same date, then the one with the later/largest sample ID will be used.
- If there is no measurement for a given parameter in an analysis window, data will be considered missing for the corresponding visit.

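### The SAP labels any patient-reported outcome or MD-VAS value from Day 267 (Week 38) as Week 52, so after the early termination some forced end-of-treatment visits are tabulated as Week 52 outcomes

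*SAP*

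**What the plan says.** SAP 2.5.4 assigns values to visits by study day: "Visit windows based on days relative to the first IMP dose will be used to map the efficacy, lab, vital signs, PK and ADA". Where a window holds several values, "the scheduled measurement that is closest to the target date will be used". No maximum distance from the target is set. In Table 9, Schedule C ("Includes physician global assessments (MD-VAS), patient reported outcomes and antibodies to sarilumab/ADA") has windows for Week 12, Week 24 (Days 127–266) and Week 52 (Day 267 onward), and none for Week 32 or Week 40. Schedules A and B, which hold the GCA assessments, CRP, ESR, weight and GTI, start Week 52 at Day 323.

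The discontinuation plan in SAP 1.1 reads: "All randomized patients should stop by 12 weeks from the date of announcement to the sites". The EOT visit was to take place at the patient's earliest convenience and no later than 13 October 2020. Under protocol 10.2.2.4 the EOT visit includes the PRO questionnaires and MD-VAS. For a premature EOT visit, protocol 10.4.4 waives only the bone density test, and only within 6 months of the baseline test.

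SAP 2.3.1 limits the primary endpoint and the Week 52 GTI scores to the Week 52 Analysis set (36 of 83 patients) and leaves the remaining efficacy endpoints in ITT. SAP 2.4.7 gives descriptive statistics for PROs and MD-VAS "for the value and change from baseline at each visit (baseline, Week 12, Week 24 and Week 52", by the four treatment groups, as observed and without imputation.

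**The concern.** When nearly everyone attends Week 52, a wide window rarely matters, because the value closest to Day 365 is the real Week 52 visit. After the termination, many patients had no Week 52 visit. Their last PRO and MD-VAS values come from an EOT visit whose study day depends on when they were randomised and when the site could see them. Any such value from Day 267 is the only one in the window, so it becomes the patient's Week 52 result.

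The SAP recognises this problem elsewhere. It says that Week 52 remission is not meaningful for patients who had no opportunity to complete 52 weeks, and it applies the same limit to the Week 52 GTI scores. For bone density, SAP 2.1.3.2 says openly that the EOT value counts towards Week 52 whenever it was taken. PROs and MD-VAS get neither the restriction nor the disclosure. A reader of the Week 52 rows would take them as one-year results, with fewer than 30 patients per group (SAP Table 1), so a few early values could shift a group mean.

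**Working it through.** **Inputs.** Target days are 169 (Week 24), 281 (Week 40) and 365 (Week 52), with the Week 52 bounds from Table 9. The EOT deadline is 13 October 2020, with 12 weeks' notice (SAP 1.1). The Week 52 Analysis set was randomised before 16 October 2019 and has 36 of 83 patients (SAP 2.3.1), so 83 − 36 = 47 lie outside it. Recruitment was suspended on 19 March 2020 (SAP 1). Screening lasts up to 42 days (protocol 1.2). Day 1 is taken as the day of randomisation, when the first dose is scheduled.

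**Reproducing the bounds.** Each is the midpoint of adjacent targets:
- Schedule C: (169 + 365)/2 = 267.
- Schedules A and B: (281 + 365)/2 = 323.

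**How early a value can be.** Day 267 is Week (267 − 1)/7 = 38. It precedes the target by 365 − 267 = 98 days, or 14 weeks. For Day 323 the gap is 42 days, or 6 weeks.

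**Which randomisation dates are affected.**
- EOT on 13 October 2020: Day 267 corresponds to a first dose 266 days earlier, 21 January 2020. Day 323 corresponds to 322 days earlier, 26 November 2019. A first dose on 16 October 2019 gives Day 364.
- EOT at about the announcement, 13 October 2020 − 84 days = 21 July 2020: Day 267 corresponds to 29 October 2019, and 16 October 2019 gives Day 280.

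**How many patients.** No individual dates are given. The count assumes that the 47 were randomised evenly from 16 October 2019, that all were still on treatment until EOT, and that all had EOT on one date. Accrual is taken to end on 19 March 2020 (156 days, counting both ends) or on 30 April 2020, allowing 42 days of screening (198 days). Number = affected days / accrual days × 47.

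| EOT date and study days | Randomised | Days | To 19 Mar | To 30 Apr |
|---|---|---|---|---|
| 21 Jul 2020, Days 267–280 | 16–29 Oct 2019 | 14 | 4.2 | 3.3 |
| 13 Oct 2020, Days 267–322 | 27 Nov 2019–21 Jan 2020 | 56 | 16.9 | 13.3 |
| 13 Oct 2020, Days 267–364 | 16 Oct 2019–21 Jan 2020 | 98 | 29.5 | 23.3 |

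Using elapsed days instead (97 of 155 and 97 of 197), the last row is 29.4 and 23.1.

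The second row is a ceiling for Days 267–322 under even accrual, because that window spans 56 days. It is reached for any common EOT date from 1 September 2020 to the deadline (1 September 2020 − 321 days = 16 October 2019).

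**One visit, two labels.** A patient first dosed on 19 December 2019 with EOT on 13 October 2020 is seen on Day 300. That visit is Week 40 for the GCA assessment, CRP, ESR and GTI, but Week 52 for PROs and MD-VAS.

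**The case against.** The strongest reply is that the window is conventional and little depends on it. Much of this stands.

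- Day 267 is the usual midpoint, and it differs from Day 323 because PROs and MD-VAS have no Week 40 assessment. A reader might infer an arithmetic error, or a fault in the mere difference between schedules. The documents support neither.
- A reader might count every forced EOT visit on Days 267–364, about 23 to 29 patients, as mislabelled. That is too many. Days 323–364 are labelled Week 52 in Schedules A and B too, and Days 362–364 lie inside the protocol's ±3-day Week 52 visit window.
- The counts assume that nobody had already left treatment and that everyone completed the assessments. Earlier dropout would lower them.
- A reader might infer a biased PRO comparison, because Appendix B of the protocol schedules Group D on 2 to 4 mg/day of prednisone at Week 38 and 0 to 1 mg/day at Week 51. The stated PRO objective compares sarilumab with placebo on the 26-week taper, and Groups A to C are scheduled on no active prednisone at either time. Group D enters the side-by-side display and possibly MD-VAS, whose objective names no comparator. No document gives a figure for the effect on these scores.
- The tables are descriptive, with no test.

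None of this answers the labelling point. Nothing in either document excludes, separates or discloses PRO and MD-VAS values from termination visits that enter the Week 52 rows.

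**Conclusion.** The concern holds as a labelling and population problem in the descriptive Week 52 PRO and MD-VAS summaries. As written, the SAP reports forced EOT visits up to 14 weeks early as Week 52. On the assumptions of even randomisation, full retention to EOT and a common EOT date, about 3 to 4 patients (EOT about 21 July 2020) up to about 13 to 17 (EOT 13 October 2020) outside the Week 52 Analysis set would have a Day 267–322 value so labelled. Members of that set who stopped early under the plan could add to this, by a number the documents do not allow one to estimate. The primary endpoint, the Week 52 GTI scores and all p-values are untouched. The change should be made, but no main conclusion depends on it.

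**What to change.** 1. In SAP 2.3.1 and 2.4.7, restrict the Week 52 PRO and MD-VAS summaries to the Week 52 Analysis set, as 2.3.1 already does for the primary endpoint and Week 52 GTI. A new day bound alone is not enough: with EOT on 13 October 2020, Day 323 would still admit patients first dosed from 16 October to 26 November 2019.
2. Within that set, use Day 323 as the lower bound of Week 52 for PROs and MD-VAS. Schedule C also holds ADA, so give PROs and MD-VAS their own column or decide the ADA window separately.
3. Report every other EOT value after Day 266 in a separate 'premature EOT' row, with the study day summarised: Days 267–322 in any patient, and Day 323 onward in patients outside the set. A row limited to Days 267–322 would leave the latter values reported nowhere.

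The cost is one table, two short text changes and the mapping program. Fewer patients will appear in the Week 52 rows.
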